3.3.2 Control Group

The trial will not include a placebo arm because delaying coagulation factor replacement in bleeding patients may expose them to the negative consequences of excessive blood loss, is not consistent with standard practice [90] and would withhold an effective treatment from patients and thus be unethical. Moreover, the question being addressed does not meet any of Freedman's five conditions that would justify the use of a placebo control, which are: 1) no standard treatment exists; 2) standard treatment is not better than placebo; 3) standard treatment is a placebo or no treatment; 4) new evidence has shown uncertainty of the risk-benefit profile of the standard treatment; and 5) effective treatment is not readily available due to cost or supply issues [91].

3.3.3 Study Parameters

A dichotomous classification of haemostatic effectiveness will be used to assess treatment response to PCC or FP in bleeding adult cardiac surgical patients. Treatment will be considered 'effective' if no additional haemostatic intervention is required in the time window from 60 minutes to 24 hours after initiation of the first IMP dose. The 60-minute time period will allow for the administration of the IMP and establishment of treatment effect. Patients will be assigned a haemostatic treatment response classification of 'ineffective' if their management required haemostatic interventions during the time window from 60 minutes to 24 hours after initiation of the first IMP dose.

Haemostatic intervention includes the administration of any systemic haemostatic agents (including platelets, cryoprecipitate, fibrinogen concentrate, activated factor VII, other coagulation factor products, or a second dose of IMP) or any haemostatic interventions (including surgical re-opening for bleeding). Because of the complexity and dynamic nature of cardiac surgery, as well as the multifactorial nature of haemorrhage during cardiac surgery, it is inherently not feasible to assess the specific haemostatic response to individual therapeutic agents.

The following secondary endpoints will be included to provide supportive evidence of haemostatic efficacy: global haemostatic response, INR reduction, the incidence and amount of individual allogeneic blood components transfused and the incidence of other bleeding-related clinical endpoints.

Global haemostatic response will be based on the haemostatic efficacy scale used successfully in a Phase 3b RCT by Sarode and colleagues [69] (in discussion with the Food and Drug Administration), modified to reflect the special considerations of haemorrhage during cardiac surgery.

4 STUDY POPULATION

4.1 Population Base

The study will include approximately 500 randomised bleeding adult (≥ 18 years old) cardiac surgical patients who require coagulation factor replacement after CPB. The study will continue until there are at least 410 evaluable patients, accounting for dropouts in both arms, with a minimum of 205 patients assigned to each of the two treatment groups.

4.1.1 Inclusion Criteria

Patients undergoing the following criteria will be eligible for inclusion in the study:

1. Adult (≥ 18 years old) patients undergoing any index cardiac surgery employing CPB
2. Coagulation factor replacement with PCC or FP ordered in the operating room for:
 - a. Management of bleeding, or
 - b. Anticipated bleeding in a patient who has been on-pump for >2 hours or undergone a complex procedure (e.g., aortocoronary bypass [ACB] plus aortic valve replacement)
3. Coagulation factor deficiency, either known to exist (e.g., as indicated by elevated EXTEM clotting time [CT] or INR) or suspected based on the clinical situation
4. Patients who have given written informed consent³

4.1.2 Exclusion Criteria

Patients who meet any of the following criteria are *not* eligible for the study:

1. Undergoing heart transplantation, insertion or removal of ventricular assist devices (not including intra-aortic balloon pump [IABP]) or repair of thoracoabdominal aneurysm
2. Critical state immediately before surgery with high probability of death within 24 hours of surgery (e.g., acute aortic dissection, cardiac arrest 24 hours before surgery)
3. Severe right heart failure (clinical diagnosis \pm echocardiography)
4. Known contraindications to heparin
5. PCC required for reversal of warfarin or direct oral anticoagulant (DOAC; dabigatran, rivaroxaban, apixaban or edoxaban) within 3 days prior to or during surgery
6. Known TEE within 3 months prior to surgery
7. History of severe allergic reactions to PCC or FP
8. Individuals who have IgA deficiency with known antibodies against IgA
9. Refusal of allogeneic blood products

³ In Canada, informed consent will be obtained after randomisation, in accordance with Article 3.7A of the 2018 Tri-Council Policy Statement on the Ethical Conduct for Research Involving Humans.

10. Known pregnancy
11. Currently enrolled in any other interventional clinical trials

4.2 Prior and Concomitant Therapy

Details on medications taken within 1 week before enrolment and concomitant medications taken during the study (excluding drugs given for routine anaesthesia) will be recorded in the case report form (CRF).

4.2.1 Permitted Concomitant Therapy

Participating hospitals will use a standardised point-of-care based transfusion algorithm that will employ a targeted approach to correct coagulopathy (as per the validated TACS algorithm) [79], but with selection of PCC or FP determined according to the patient's assigned grouping and using the doses described in **Section 5.4**.

Concomitant administration of any therapies required as part of standard patient care is permitted but must be recorded in the CRFs. All haemostatic drugs or products administered (e.g., heparin and protamine dose, antifibrinolytic drugs, desmopressin, rFVIIa, idarucizumab, andexanet alpha or topical haemostatic agents) will be recorded, as well as all procedures that may influence amount of bleeding (e.g., retrograde autologous priming of CPB circuit, cell salvage). In addition, concomitant medications used to treat SAEs will be reported throughout the duration of follow-up (up to POD-30).

4.2.2 Forbidden Concomitant Therapy

No concomitant therapies are forbidden.

4.3 Withdrawal and Replacement of Patients

4.3.1 Premature Subject/Patient Withdrawal

Patients have the right to withdraw from the study at any time for any reason, without the need to justify their decision. The Investigator also has the right to withdraw patients for reasons such as intervention no longer indicated due to cessation of bleeding, randomisation of ineligible patients and adverse events attributed to previous doses of IMP. For any withdrawals after study entry, the Investigator will obtain all the required details and document the reason(s) for discontinuation, and report to the IDSMC and institutional review board (IRB) where indicated. If the reason for withdrawal of a patient is an AE, the main specific event or laboratory test will be recorded, and the Investigator will make thorough efforts to clearly document outcomes up to the time of withdrawal of participation.

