3.1.3 Safety Endpoints

All AEs and serious AEs (SAEs) will be collected from beginning of surgery (defined as entry into OR) to POD-30.

1. Comparison of the incidence of serious treatment-emergent adverse events (TEAEs), individually and as composite where appropriate (e.g., TEEs, major adverse cardiac events), between the *Octaplex* and FP groups.
2. Comparison of the duration of mechanical ventilation (measured as duration of ventilation and ventilator-free days) up to POD-30 between the *Octaplex* and FP groups.
3. Comparison of the duration of ICU stay up to POD-30 between the *Octaplex* and FP groups.
4. Comparison of the duration of hospitalisation up to POD-30 between the *Octaplex* and FP groups.
5. Comparison of the incidence of death up to POD-30 between the *Octaplex* and FP groups.
6. Comparison of the number of days alive and out of hospital at POD-30 between the *Octaplex* and FP groups.

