7.3.2 Adverse Events (AEs)

7.3.2.1 Definitions

- **Adverse event (AE):** An AE is any untoward medical occurrence in a study patient receiving an IMP and which does not necessarily have a causal relationship with this treatment. An AE can therefore be any unfavourable and unintended sign (including an abnormal laboratory finding), symptom or disease temporally associated with the use of an IMP, whether or not related to the IMP. An AE is defined as a treatment-emergent AE (TEAE) if first onset or worsening is after the first treatment with study drug.
- **Adverse drug reaction (ADR):** An ADR is any noxious and unintended response to an IMP related to any dose. The phrase 'response to an IMP' means that a causal relationship between the IMP and an AE carries at least a reasonable possibility, i.e., the relationship cannot be ruled out.

- **Other significant AEs:** Any marked laboratory abnormalities or any AEs that lead to an intervention, including withdrawal of drug treatment, dose reduction or significant additional concomitant therapy.
- **Withdrawal due to AE/ADR:** AE/ADR leading to discontinuation of treatment with IMP. Any such events will be followed up by the Investigator until the event is resolved or until the medical condition of the patient is stable. All follow-up information collected will be made available to the Sponsor.

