7.3.2.6 Outcome of AEs

The outcome of all reported AEs has to be documented as follows:

1. Recovered, resolved
2. Recovering, resolving
3. Not recovered, not resolved
4. Recovered, resolved with sequelae
5. Fatal
6. Unknown

NOTE: A patient's **death** per se is not an event, but an outcome. The event which resulted in the patient's death must be fully documented and reported, even in cases where the

death occurs within 4 weeks after IMP treatment end and regardless of whether or not it is considered treatment related.

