7.3.2.7 Action(s) taken

AEs requiring action or therapy must be treated with recognised standards of medical care to protect the health and well-being of the patient. Appropriate resuscitation equipment and medicines must be available to ensure the best possible treatment in an emergency situation.

The action taken by the Investigator must be documented:

a) General actions taken in the event of an AE

- None
- Medication (other than IMP) or other (e.g., physical) therapy started
- Test performed
- Other (to be specified)

b) IMP-related actions taken in the event of an AE

- None
- Product withdrawn
- Dose reduced
- Dose increased

The Investigator will follow up on each AE until it has resolved or until the medical condition of the patient has stabilised. Any relevant follow-up information will be reported to the Sponsor.

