Other than abnormal laboratory values due to the underlying condition, the Investigator must assess the clinical significance of abnormal laboratory values outside the specified normal range. Any clinically significant abnormalities will be documented. All specified clinically significant abnormalities will be documented as AEs/SAEs and investigated.

Additional tests and other evaluations required to establish the significance or aetiology of specified abnormalities or to monitor the course of an AE will be obtained if clinically indicated. Follow-up will persist until resolution or up to the Study Completion Visit, whichever occurs first.

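### Protocol 4.3.1 does not separate stopping IMP from leaving the study, so POD-30 safety follow-up is not secured for treated patients withdrawn because of an attributed adverse event

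*Protocol*

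**What the plan says.** Protocol Section 4.3.1 gives the Investigator a right to withdraw patients. Besides cessation of bleeding, the reasons listed include "randomisation of ineligible patients and adverse events attributed to previous doses of IMP". Where an AE is the reason, the event is recorded and "the Investigator will make thorough efforts to clearly document outcomes up to the time of withdrawal of participation". Nothing is said about the period after that.

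Two other places show that withdrawal here can mean leaving the study. Section 4.3.2 speaks of patients withdrawn from the study for safety reasons, and Section 9.2.3.1 plans tables of TEAEs that resulted in withdrawal from the study.

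The safety sections ask for more than 4.3.1 does:

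- Section 3.1.3: AEs and SAEs "will be collected from beginning of surgery (defined as entry into OR) to POD-30". Section 6 repeats that AEs and SAEs are recorded until POD-30.
- Section 7.3.2.1, on an AE that leads to IMP discontinuation: "Any such events will be followed up by the Investigator until the event is resolved or until the medical condition of the patient is stable".
- Section 7.3.2.7: "The Investigator will follow up on each AE until it has resolved or until the medical condition of the patient has stabilised".
- Section 7.3.2.6 wants the event behind a death documented and reported, including where the "death occurs within 4 weeks after IMP treatment end and regardless of whether or not it is considered treatment related".

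On abnormal laboratory values, Section 7.3.6.2 sets a different end point: "Follow-up will persist until resolution or up to the Study Completion Visit, whichever occurs first".

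**The concern.** IMP consists of at most two doses within 24 hours, while the safety endpoints run to POD-30. A decision to give no second dose therefore need not end observation, which continues for about four more weeks. Section 4.3.1 joins the two. A site that follows it literally may stop collecting data on a treated patient because the Investigator suspects the product caused harm.

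That would be informative loss. The patients affected are chosen on a safety outcome, and the choice is made by clinicians who know the product once the seal is broken (Protocol 3.3.1.6 and 5.6). Attribution, and hence withdrawal, could differ by arm.

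The analysis plan offers no protection. Protocol 9.2.4 does not impute in general, and SAP 7.1.2 limits possible multiple imputation to the primary endpoint. The only stated rule for discontinuation belongs to the primary estimand (SAP 10.1). SAP Section 11 has no rule for patients who leave before POD-30. At stake are the comparisons of serious TEAEs, TEEs, death, ventilation, ICU stay, hospital stay, and days alive and out of hospital.

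**Working it through.** The point disputes no figure in the plan, so the main check is a comparison of text. For a treated patient withdrawn by the Investigator for an attributed AE, with consent intact, I asked of each item whether some passage requires its collection to POD-30.

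1. **The event that led to withdrawal.** Sections 7.3.2.1 and 7.3.2.7 require follow-up until resolved or stable. Section 7.3.2.1 is worded for discontinuation of IMP, whereas 4.3.1 refers to withdrawal of participation, but 7.3.2.7 covers each AE. Largely secured.
2. **A new AE, SAE or TEE after withdrawal.** Section 3.1.3 sets the window to POD-30 without an exception for withdrawn patients, and Section 7.3.5 requires all TEEs to be reported as SAEs. However, 4.3.1 asks for outcomes only up to withdrawal, and Section 7.3.7(a) says that active monitoring for post-study SAEs is not required. A site could treat the patient as post-study. Contradictory, so not secured.
3. **Death.** Section 7.3.2.6 says how a fatal event is documented and reported. It schedules no contact that would discover one. Not secured.
4. **Ventilation, ICU and hospital stay, days alive and out of hospital.** These are collected at Visits 3 and 4 (Sections 6.1.4 and 6.1.5). No passage says that those visits take place after an Investigator withdrawal. Not secured.
5. **Comparison group.** Randomised but untreated patients are followed for 30 days (Sections 3.3.1.7 and 9.2.1), and cessation of bleeding, a common reason for non-treatment, is itself a withdrawal reason in 4.3.1. Treated patients withdrawn for an attributed AE have no equivalent statement.
6. **Primary endpoint.** SAP 10.1, Table 1, counts discontinuation or death before the end of the 24-hour period as non-response, and keeps the response as valid if discontinuation comes later. Nothing is left missing by this route.

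**Scale, under assumptions only.** Neither document gives an AE-withdrawal rate. Let w be the share of an arm withdrawn for an AE, and q the share of those whose POD-30 event of a given type goes unrecorded. The fall in that arm's observed incidence is w × q. With 205 evaluable patients per arm (410 in total, Section 9.1):

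- w = 1%, q = 10%: 205 × 0.01 = 2.1 patients; fall 0.01 × 0.10 = 0.1 percentage points.
- w = 2%, q = 30%: 205 × 0.02 = 4.1 patients; fall 0.02 × 0.30 = 0.6 points.
- w = 5%, q = 50%: 205 × 0.05 = 10.3 patients; fall 0.05 × 0.50 = 2.5 points.

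Each patient whose event is missed lowers the arm's observed incidence by 1/205 = 0.49 points. For orientation, the pilot TEE rates quoted in Section 1.1 (7.4% with PCC, 8.2% with FP) differ by 0.8 points. The values of w and q are chosen to show a range and are not estimates.

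**Laboratory follow-up.** Section 7.3.6.2 stops at resolution or the completion visit, whichever is first. Section 7.3.2.2 continues until values are normal or explained, and 7.3.2.7 until the event is resolved or the patient stable. Section 6.1.5 allows follow-up beyond POD-30 where an ongoing AE calls for it. The rules differ in wording, but 6.1.5 largely covers a finding still open at POD-30, and no POD-30 comparison depends on it.

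**The case against.** A reader might infer that patients withdrawn for an attributed AE simply lose their 30-day safety follow-up. The documents do not support that. Section 4.3.1 states a duty up to withdrawal; it does not order collection to stop. The only express stop is Section 10.3, where the patient withdraws consent, and SAP 6.3 limits use of data in the same situation. Section 3.1.3 makes no exception for withdrawn patients. Cessation of bleeding appears in the same list of withdrawal reasons, yet patients left untreated for that reason are followed for 30 days, so a reason listed in 4.3.1 does not by itself end follow-up. The phrase about previous doses also suggests that the authors may mainly have had the second dose in mind.

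The bias is limited in another way. SAP 11.1 counts a patient once within a preferred term or organ class, so someone withdrawn for a TEE is already counted as having had one. An event is lost only if it is of a different kind, occurs after withdrawal, and is not collected despite Section 3.1.3.

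All of this stands, and it rules out calling the loss certain. It does not tell a site which instruction prevails, and it does not secure the contact or the duration data.

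**Conclusion.** The point holds as an inconsistency that leaves a gap in safety follow-up. Section 4.3.1 conflicts with Sections 3.1.3, 7.3.2.1 and 7.3.2.7. For treated patients withdrawn on suspicion of product harm, it leaves the POD-30 contact, new events, vital status and the duration endpoints unsecured while consent stands. The index event is largely covered.

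The safety comparisons could be biased by informative loss. Neither its occurrence nor its direction between arms is established. The size cannot be derived; the range of 0.1 to 2.5 percentage points rests wholly on assumed withdrawal and event shares. A reader might also want to state the loss as a share of expected TEEs. That would need the same unsupported rates, and later deaths could not be set against TEEs alone. The primary analysis is unaffected. The laboratory follow-up wording is a minor matter.

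**What to change.** Amend Protocol 4.3.1 so that an Investigator decision to give no further IMP, for whatever listed reason, is recorded as IMP discontinuation. State that all treated patients then remain in AE/SAE, TEE, survival, ventilation, ICU and hospital-stay follow-up to POD-30, unless the patient withdraws consent (or, at Canadian sites, refuses it, as Section 9.2.1 already provides). Align Sections 4.3.2 and 9.2.3.1 with that distinction.

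As a minor wording point, reconcile the follow-up end point in Section 7.3.6.2 with Sections 6.1.5, 7.3.2.1, 7.3.2.2 and 7.3.2.7.

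The change leaves untouched when and why IMP is stopped. It uses the POD-30 contact, in person or by phone, that is already scheduled as Visit 4. The cost is protocol wording and a few more contacts to complete.

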4.3.2 Subject/Patient Replacement Policy

Patients withdrawn from the study for safety reasons will not be replaced.

4.4 Assignment of Patients to Treatment Groups

Patients will be assigned to treatment with either PCC or FP using a permuted-block, stratified (by centre) random allocation scheme prepared by a biostatistician not involved in the conduct of the trial. Group allocation will apply to the first two doses of IMP during the treatment period (up to 24 hours from IMP initiation). For any additional doses (i.e., the

third dose and thereafter), patients in both groups will receive FP. Patients are not permitted to re-enrol in the study.

4.5 Relevant Protocol Deviations

Classification of protocol deviations as minor and major will be defined *a priori*. Patients with major protocol deviations will be excluded from the per-protocol analyses. The Sponsor and IDSMC will review the number and nature of major protocol deviations and take appropriate measures to minimise the impact on the study.

4.6 Subsequent Therapy

Any subsequent haemostatic therapy will be according to institutional standard of care.

5 INVESTIGATIONAL MEDICINAL PRODUCT(S)

5.1 Characterisation of Investigational Product(s)

5.1.1 Octaplex

Octaplex is a product derived from human plasma containing the coagulation factors II, VII, IX and X and proteins C and S. It is manufactured by chromatographic purification of cryoprecipitate-poor plasma.

The Octaplex manufacturing process includes two dedicated virus inactivation/removal steps, by way of a solvent/detergent viral inactivation process and a virus removal nanofiltration step. The solvent/detergent treatment causes enveloped viruses such as pseudorabies virus (PRV), Schmallenberg virus (SBV) and human immunodeficiency virus (HIV) type 1 to be irreversibly destroyed. Nanofiltration removal of infectious agents from protein solutions on the basis of their size may be the only method to date permitting efficient removal of enveloped (e.g., HIV-1, SBV, PRV, bovine viral diarrhoea virus) and non-enveloped viruses (e.g., hepatitis A virus) under conditions where 90–95% of protein activity is recovered [92]. Other precautions against viral transmission include: selection of plasma donors, screening of donations and plasma pool, as well as quality control measurements of the final product.

5.1.1.1 Composition of Octaplex

Octaplex is a human PCC for intravenous (IV) use. The composition of Octaplex is described in the current edition of the IB. Differences in composition may exist between countries; please refer to the country-specific Summary of Product Characteristics (SmPC) and Package Insert (PI).

5.1.2 Frozen plasma

For patients randomised to FP, the blood bank/pharmacy will assign to the study, prepare and release FP for the first and second orders received during the treatment period (24 hours after IMP initiation). The recommended dose for FP will be 3 U for patients weighing ≤ 60 kg and 4 U for patients weighing > 60 kg. While there is no maximum dose for FP, during the treatment period administration of up to 6 U for patients weighing ≤ 60 kg and up to 8 U for patients weighing > 60 kg will be counted as part of the IMP.

FP will be provided by local supplier of blood components and will be stored, thawed and pooled by the blood bank/pharmacy according to current standards. FP will be infused as per standard hospital protocols at the participating institutions (i.e., infused using timing recommended in the current monograph through standard 140 μ m blood infusing set).

